4.2. Definition of Study Drugs

Open-label treatment period

All subjects will receive TD-9855 [REDACTED] starting on Day 2 through the end of the treatment period.

Randomized treatment period

Subjects will be randomized in a 1:1 ratio to receive either TD-9855 (test product) or placebo (reference product) once daily starting in the morning post randomization (Day 2) through the end of the treatment period.

4.3. Sample Size Considerations

[REDACTED]

4.5. Clinical Assessments

Study Period:	Screening ^a (De Novo Group Only – in clinic)	Open Label Treatment (Visits either in clinic or remote for each subject)						Randomized Withdrawal Period (For each subject, Visits 6 through 9, all either in clinic or remote)				Follow-up ^c
	Study Day (Visit):	-28 to -7 (Visit S)	Day 1 (Visit 1) ^b	Day 15 (Visit 2) +/- 3 days	Day 29 (Visit 3) +/- 3 days	Day 57 (Visit 4) +/- 3 days	Day 85 (Visit 5) +/- 3 days	Day 113 (Visit 6) +/- 3 days	Day 127 (Visit 7) +/- 3 days	Day 141 (Visit 8) +/- 3 days	Day 155 (Visit 9) / ET +/- 3 days	Day 169 (Visit 10) +/- 3 days
Procedure												
Informed consent ^d	X	X										
Inclusion /exclusion criteria ^d	X	X ^e										
Medical history (including smoking history) ^f	X											
Concomitant medications (including smoking usage)	X ^f	X ^e	X	X	X	X	X	X	X	X	X	X
MoCA	X											
OHQ subject training ^g	X	X ^e		X	X	X	X	X	X	X	X	
OHQ (OHSA and OHDAS)		X ^e		X	X	X	X	X	X	X	X	
PGI-S		X ^e		X	X	X	X	X	X	X	X	
C-SSRS	X	X ^e		X	X	X	X	X	X	X	X	X
Tilt-table test ^h	X											
Randomization ⁱ							X					
Recommended Order of Procedures (when applicable)												
██████		■				■		■			■	
██████		■				■		■			■	
██████ ████████		■				■		■			■	
██████████████████		■				■		■			■	
██████████████████		■				■		■			■	
██████		■				■		■			■	

Study Period: Study Day (Visit):	Screening ^a (De Novo Group Only – in clinic)	Open Label Treatment (Visits either in clinic or remote for each subject)					Randomized Withdrawal Period (For each subject, Visits 6 through 9, all either in clinic or remote)				Follow-up ^c
	-28 to -7 (Visit S)	Day 1 (Visit 1) ^b	Day 15 (Visit 2) +/- 3 days	Day 29 (Visit 3) +/- 3 days	Day 57 (Visit 4) +/- 3 days	Day 85 (Visit 5) +/- 3 days	Day 113 (Visit 6) +/- 3 days	Day 127 (Visit 7) +/- 3 days	Day 141 (Visit 8) +/- 3 days	Day 155 (Visit 9) / ET +/- 3 days	Day 169 (Visit 10) +/- 3 days
██████████		■			■		■			■	
██████████		■			■		■			■	
██████████		■		■	■	■	■	■	■	■	
██████████ ████	■	■		■	■	■	■	■	■	■	
Vital signs (BP, HR, RR and body temperature) ^l	X	X ^e	X	X	X	X	X	X	X	X	X
Height (cm)	X										
Weight (kg)	X	X ^e					X			X	X
Physical examination ^m	X	X ^e	X				X			X	
Neurological examination	X	X ^e					X			X	
12-lead electrocardiogram ⁿ	X	X ^e		X			X			X	
Pregnancy test ^o	X	X ^e					X			X	
Norepinephrine (NE)	X										
Safety laboratory test (chemistry, hematology, and urinalysis)	X	X ^e	X		X		X			X	
██████████ ████					■		■	■			
██████████		■			■						
██████████											
ESC (for confirmation of diagnosis) ^a	X										
24-hour ambulatory BP device provision ^f	X	X ^e		X							

Study Period:	Screening ^a (De Novo Group Only – in clinic)	Open Label Treatment (Visits either in clinic or remote for each subject)					Randomized Withdrawal Period (For each subject, Visits 6 through 9, all either in clinic or remote)					Follow-up ^c
	Study Day (Visit):	-28 to -7 (Visit S)	Day 1 (Visit 1) ^b	Day 15 (Visit 2) +/- 3 days	Day 29 (Visit 3) +/- 3 days	Day 57 (Visit 4) +/- 3 days	Day 85 (Visit 5) +/- 3 days	Day 113 (Visit 6) +/- 3 days	Day 127 (Visit 7) +/- 3 days	Day 141 (Visit 8) +/- 3 days	Day 155 (Visit 9) / ET +/- 3 days	Day 169 (Visit 10) +/- 3 days
24-hour ambulatory BP device collection ^f		X ^e	X		X							
Wearable device provision/collection ^s	X	X ^e		X	X	X	X	X	X	X		
Incidence of Falls and ABPM position Diaries	X	X ^e	X	X	X	X	X	X	X	X		
Dosing and Midodrine rescue medication Diaries		X ^e	X	X	X	X	X	X	X	X		
Adverse events	X	X ^e	X	X	X	X	X	X	X	X	X	
Dispense study medication		X ^e										
Study medication dosing ^t		X										
Collect, review, and dispense study medication				X	X	X	X	X	X			
Collect and review study medication										X		
Valsalva maneuver ^u	X											

Abbreviations: [REDACTED]; BP: Blood Pressure; [REDACTED]; C-SSRS: Columbia Suicide Severity Rating Scale; ESC: Enrollment Steering Committee; ET: Early Termined; [REDACTED]; [REDACTED]; HR: Heart Rate; MoCA: Montreal Cognitive Assessment; MSA: Multiple System Atrophy; [REDACTED]; OHDAS: Orthostatic Hypotension Daily Activity Scale; OHSA: Orthostatic Hypotension Symptom Assessment; OHQ: Orthostatic Hypotension Questionnaire; OL: Open Label; PAF: Pure Autonomic Failure; PD: Parkinson’s Disease; [REDACTED] PGI-S: Patient Global Impression of Severity; RTSM: Randomization and trial supply management; RR: Respiratory Rate; UMSARS: [REDACTED]; [REDACTED]

- a. [REDACTED] Subject eligibility will be assessed by the investigator during screening and primary diagnosis will be verified by the ESC prior to Day 1 (for De Novo Group subjects only); subjects meeting OHSA#1 criterion on Day 1 and who otherwise meet eligibility criteria may be enrolled via RTSM.
- b. For 0169 Completers Group, Study 0169 procedures conducted at D29 will serve as the baseline assessments for D1 of Study 0170.

blood pressure measurement. Details regarding the ambulatory monitoring will be provided in a separate manual. The assessment on D1 is only for De Novo Group subjects.

- s. For wearables, in countries where the wearable devices are available, 2 consecutive days of device usage will be required on the days shown. The 2 consecutive days of device usage should take place within 5 days before the subsequent visit. Site coordinators will monitor subject compliance. If the site coordinator becomes aware that a subject has not performed the required device usage, they will contact the subject and remind them to use the device.
- t. Study medication will be ingested orally without regard to food at approximately the same time each morning and taken with approximately 8 ounces of water. The exact time and day of dosing will be recorded by the subject in the Dosing Diary on the mornings of study visits. During their scheduled visits, subjects should be reminded to maintain an adequate fluid intake. For OL treatment period, subjects would start taking medications starting on Day 2.
- u. Valsalva maneuver is to be performed for PAF subjects only if no results are available within 24 months from the date of randomization.

5. TIMING OF PLANNED ANALYSES

The analyses will occur when all subjects have completed or terminated early from the study and the database has been cleaned and locked. [REDACTED]

6. CONSIDERATIONS FOR DATA ANALYSES AND HANDLING

All data from both scheduled and unscheduled visits will be presented in data listings.

However, unless noted otherwise, only data from visits (scheduled or unscheduled) that fall within analysis windows will be included in summaries, statistical analyses, and calculation of derived variables. [REDACTED] 5.

Analyses and tabulations will be prepared [REDACTED]

Summary tables and listings will be prepared according to ICH Guideline E3 and will include a “footer” providing explanatory notes.

6.1. Columns

Separate summaries will be provided for the open-label treatment period and the randomized withdrawal treatment period. For the open-label treatment period, summary tables will include the following columns:

- Placebo Study 0169 Completers (“0169 Placebo Rollover”)
- Amprexetine Study 0169 Completers (“0169 Amp Rollover”)
- De Novo Subjects (“De Novo”)
- All Subjects (“Total”)

For the randomized withdrawal treatment period, summary tables will include the following columns:

- Placebo (“Placebo”)
- Amprexetine (“TD-9855 10mg”)
- All Subjects (required only for study population and compliance summaries) (“Total”)

6.2. Analysis Sets

6.2.1. [REDACTED]

[REDACTED]

6.2.2. Enrolled Analysis Set

The enrolled analysis set comprises all subjects who were enrolled into the open-label treatment period.

6.2.3. Randomized Analysis Set

The randomized analysis set comprises all subjects who were randomized into the randomized withdrawal treatment period.

6.2.4. Full Analysis Set (FAS) – OL and Safety Analysis Set – OL

The FAS and safety analysis set for the open-label treatment period are identical and comprise all enrolled subjects who received at least 1 dose of TD-9855 during the period.

6.2.5. FAS – Randomized Withdrawal and Safety Analysis Set – Randomized Withdrawal

The FAS and safety analysis set for the randomized withdrawal treatment period are identical and comprise all randomized subjects who received at least 1 dose of study medication (TD-9855 or placebo) following randomization.

6.2.6. Subject Grouping for FAS vs. Safety Analysis Set Summaries

Although the FAS and safety analysis sets for each of the 2 treatment periods are identical, subject grouping for randomized withdrawal period analysis may differ. For safety analysis set analyses, subjects will be grouped according to the study treatments they received. For FAS analyses, subjects will be grouped according to the study treatments they were randomized to receive.

6.2.7. Per-Protocol (PP) Analysis Set – Randomized Withdrawal

A PP analysis set is defined for the randomized withdrawal treatment period, and comprises all subjects in the FAS – Randomized Withdrawal analysis set except those who meet any of the following criteria:

- Received wrong treatment during the randomized withdrawal treatment period
- Study medication compliance < 80% over the interval from first to last dose of the randomized withdrawal treatment period
- Did not meet certain efficacy-related inclusion criteria, specifically:
 - Inclusion criterion 4 for De Novo subjects (Subject must meet the diagnostic criteria of nOH, as demonstrated by a sustained reduction in BP of ≥ 20 mmHg (systolic) or ≥ 10 mmHg (diastolic) within 3 min of being tilted up $\geq 60^\circ$ from a supine position as determined by a tilt-table test.)
 - Inclusion criterion 5 for De Novo subjects (Subject must score at least a 4 on the OHSA#1 at V1.)

- Continuation Criterion (At V3 / Week 4, following the initial 4-week open-label treatment, subjects must show a reduction in OHSA#1 of at least 2 points compared to the baseline value, as determined in Study 0169 for subjects entering from Study 0169 and from V1 for De Novo subjects, to continue in Study 0170.)
- Randomization Criterion for randomized withdrawal treatment period (Subject has OHSA#1 score of ≤ 7 .)
- Used efficacy-related prohibited concomitant medications during the randomized withdrawal treatment period

6.2.8. Subgroups

To assess consistency of treatment effect across subgroups, the following subgroups will be examined:

- Disease type: MSA, PD, and PAF
- Gender: Male and Female
- Baseline NE: < 200 pg/mL and ≥ 200 pg/mL

The disease type and gender subgroups were specified in the protocol. Smoking status subgroups were also specified in the protocol, but too few current smokers were enrolled to warrant summaries by smoking status. The dichotomized baseline NE subgroups were added because a post hoc analysis of Study 0169 indicated that for some endpoints the effect of TD-9855 on the endpoint may vary with baseline norepinephrine level. For both open-label treatment period and randomized withdrawal treatment period summaries, these subgroups will be defined using the open-label NE baseline value (Section 6.3.1). COVID-19 pandemic onset subgroups (COVID-19 pandemic onset: subjects whose week 22 visit occurred before 18MAR2020 and subjects whose week 22 visit occurred on or after 18MAR2020) were added to explore pandemic effects on data collection and subjects' daily activities and later dropped because not enough week 22 visits (only 7) occurred before 18MAR2020.

6.3. Baseline Definition

For the open-label treatment period of the study, the baseline is the Study 0169 V6 (Week 4) assessment for subjects entering from Study 0169 and the V1 assessment for De Novo subjects. If a V1 assessment was not obtained for De Novo subjects, the latest earlier assessment will be used.

The assessments obtained at the Week 16 (V6, D113) visit in the open-label treatment period prior to randomization are considered the baseline assessments for the randomized withdrawal treatment period of the study.

Two variables have special baseline definitions, norepinephrine and smoking status. Details are given in the following sections.

6.3.1. Norepinephrine (NE)

For De Novo subjects, NE was collected during screening to confirm eligibility to enroll in Study 0170. Subjects were required to have a resting seated value ≥ 100 pg/mL. For pharmacodynamic analyses, NE blood samples were to be collected for all subjects on Day 1 and Day 57. These pharmacodynamic samples were to be collected after the subject had been seated for 30 minutes and were to be collected at approximately the same time of day on Day 1 and Day 57.

Baseline NE for the open-label period was defined as follows:

- For subjects rolling over from Study 0169, the Study 0169 baseline result, which was the last NE result obtained before the first dose of study medication in Study 0169
- For De Novo subjects, the last NE result obtained before the first dose of study medication in Study 0170 (i.e., the screening result)

Baseline NE for the randomized withdrawal treatment period was defined as the last NE result obtained after the first dose of open-label study medication in Study 0170 and before the first dose of randomized study medication (i.e., as the Day 57 result).

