		Day 1 (Visit 1) ^b	Day 15 (Visit 2) +/- 3 days	Day 29 (Visit 3) +/- 3 days	Day 57 (Visit 4) +/- 3 days	Day 85 (Visit 5) +/- 3 days	Day 113 (Visit 6) +/- 3 days	Day 127 (Visit 7) +/- 3 days	Day 141 (Visit 8) +/- 3 days	Day 155 (Visit 9) / ET +/- 3 days	Day 169 (Visit 10) +/- 3 days	
Procedure												
Informed consent ^d	X	X										
Inclusion /exclusion criteria ^d	X	X ^e										
Medical history (including smoking history) ^f	X											
Concomitant medications (including smoking usage)	X ^f	X ^e	X	X	X	X	X	X	X	X	X	X
MoCA	X											
OHQ subject training ^g	X	X ^e	X	X	X	X	X	X	X	X	X	
OHQ (OHSA and OHDAS)		X ^e	X	X	X	X	X	X	X	X	X	
PGI-S		X ^e	X	X	X	X	X	X	X	X	X	
C-SSRS	X	X ^e	X	X	X	X	X	X	X	X	X	X
Tilt-table test ^h	X											
Randomization ⁱ							X					
Recommended Order of Procedures (when applicable)												
NMSS		X ^e			X		X				X	
HADS		X ^e			X		X				X	
UPDRS ^j (PD Subjects only)		X ^e			X		X				X	
PDQ-8 (PD Subjects only)		X ^e			X		X				X	
UMSARS (MSA Subjects only)		X ^e			X		X				X	

SCHEDULE OF STUDY PROCEDURES (CONTINUED)

Table 1: Schedule of Study Procedures

Study Period:	Screening ^a (De Novo Group Only – in clinic)	Open Label Treatment (Visits either in clinic or remote for each subject)						Randomized Withdrawal Period (For each subject, Visits 6 through 9, all either in clinic or remote)				Follow-up ^c
		Day 1 (Visit 1) ^b	Day 15 (Visit 2) +/- 3 days	Day 29 (Visit 3) +/- 3 days	Day 57 (Visit 4) +/- 3 days	Day 85 (Visit 5) +/- 3 days	Day 113 (Visit 6) +/- 3 days	Day 127 (Visit 7) +/- 3 days	Day 141 (Visit 8) +/- 3 days	Day 155 (Visit 9) / ET +/- 3 days	Day 169 (Visit 10) +/- 3 days	
COMPASS-31 (MSA Subjects only)		X ^e			X		X			X		
EQ-5D-5L		X ^e			X		X			X		
BSFC-s		X ^e		X	X	X	X	X	X	X		
Orthostatic standing test ^k	X	X ^e		X	X	X	X	X	X	X		
Vital signs (BP, HR, RR and body temperature) ^l	X	X ^e	X	X	X	X	X	X	X	X	X	
Height (cm)	X											
Weight (kg)	X	X ^e					X			X	X	
Physical examination ^m	X	X ^e	X				X			X		
Neurological examination	X	X ^e					X			X		
12-lead electrocardiogram ⁿ	X	X ^e		X			X			X		
Pregnancy test ^o	X	X ^e					X			X		
Norepinephrine (NE)	X											
Safety laboratory test (chemistry, hematology, and urinalysis)	X	X ^e	X		X		X			X		
Pharmacokinetic sampling ^p					X		X	X				
Pharmacodynamic sampling ^q		X ^e			X							

SCHEDULE OF STUDY PROCEDURES (CONTINUED)

Table 1: Schedule of Study Procedures

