6.4.8. Pharmacodynamic Assessments

At the time points described in the Schedule of Study Procedures ([Table 1](#)), blood samples for pharmacodynamic markers may be measured. Detailed instructions and collection kits for sample collection, handling, and shipping will be provided in the laboratory manual.

Blood samples for pharmacodynamic markers (DHPG and NE) will be collected at select study visits as defined in the Schedule of Study Procedures after the subject has been seated for 30 minutes. Note that all pharmacodynamic marker samples should be collected at approximately (± 1 hour) the same time of day. Time-matched sampling will enable time-matched analysis, which is critical for biomarkers of the NE pathway owing to diurnal variations. NE alone will also be collected at Screening Visit as part of the eligibility criteria evaluations.

Assessments will be performed as specified in the Schedule of Study Procedures ([Table 1](#)).

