8. STATISTICAL CONSIDERATIONS

8.1. General Considerations

All data for each subject will be listed as collected. All statistical summaries and analyses will be performed using SAS software (SAS Institute, Cary, North Carolina, US).

Continuous data will be summarized using an 8-point descriptive summary (n, mean, standard deviation, median, interquartile range [25% quartile, 75% quartile], minimum, and maximum) unless otherwise specified in the statistical analysis plan (SAP) or table shell. Categorical data will be summarized using counts and percentages.

For analysis, Day 1 is defined as the day of the first study medication dose. The preceding day is Day -1.

Baseline is the last assessment (scheduled or unscheduled) obtained before start of study medication dosing for each phase of the study (OL or double-blind randomized withdrawal phase), unless otherwise specified in the SAP. Baseline for endpoints that have more than one component is calculated from the individual component baselines, whether or not they were assessed during the same visit.

Any changes to the data summaries and analyses outlined in this section will be described in the applicable SAP. Any changes to the definition of the endpoints will also be included in a protocol amendment.

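### Does the SAP leave open which norepinephrine sample is the open-label baseline for De Novo subjects?

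*SAP*

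**What the plan says.** SAP section 6.3.1 first describes the samples. De Novo subjects have NE measured at screening to confirm the eligibility floor of 100 pg/mL, and for pharmacodynamic purposes "NE blood samples were to be collected for all subjects on Day 1 and Day 57".

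It then sets the open-label baseline. Rollover subjects take their Study 0169 baseline, the last result before their first dose in that study. For the other group the text reads "For De Novo subjects, the last NE result obtained before the first dose of study medication in Study 0170 (i.e., the screening result". The randomized-withdrawal baseline has the same form, the last result after open-label dosing starts and "before the first dose of randomized study medication (i.e., as the Day 57 result".

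Two general rules stand nearby. SAP section 6.3 makes Visit 1 the open-label baseline for De Novo subjects and adds: "If a V1 assessment was not obtained for De Novo subjects, the latest earlier assessment will be used". It then lists NE as one of two variables with special baseline definitions. Protocol section 8.1 says "Baseline is the last assessment (scheduled or unscheduled) obtained before start of study medication dosing for each phase of the study", but lets the SAP override this.

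SAP section 6.2.8 uses open-label baseline NE to form subgroups below and at or above 200 pg/mL in both periods. Sections 8.4.1 and 8.5 repeat the primary and secondary analyses in those subgroups.

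**The concern.** The bracket in the De Novo bullet equates two things that the schedule makes different. A Day 1 sample exists by design and precedes the first dose, so the last pre-dose result should be Day 1 and not screening. One programmer working from the rule and another from the bracket would build different baselines. The Day 57 sentence in the same section has the same form but causes no trouble, because only one scheduled sample falls in its interval.

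If the choice were truly open, it could move De Novo subjects across the 200 pg/mL cut and so alter the NE rows of the primary-endpoint forest plot. SAP section 6.2.8 says these subgroups were added after a post hoc look at Study 0169. A question that was itself suggested by data is one where analysts should have little room to choose.

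**Working it through.** The plan gives no figure on this point to reproduce. The check is a timeline, a reading of the text, and an illustration of size.

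**1. Timeline for a De Novo subject**

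| NE sample | Timing | Source |
|---|---|---|
| Screening | 7 to 28 days before Day 1 | Protocol 6.3.1 |
| Day 1 | within 24 hours before the first dose | Protocol Table 1, footnotes e and q |
| First open-label dose | morning of Day 2 | Protocol Table 1, footnote e |
| Day 57 | on open-label treatment | Protocol Table 1, footnote q |

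With a Day 1 result, the last pre-dose result is Day 1 whether screening fell on Day -28 or Day -7, and rule and bracket disagree. Without one it is screening, and they agree. Day 1 results can be absent: the protocol synopsis limits pharmacodynamic sampling to consenting subjects, and protocol section 6.4.8 says "blood samples for pharmacodynamic markers may be measured".

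**2. Which sample the SAP points to**

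- The bracket names screening outright.
- NE has its own row in both schedules, ticked at screening only. The Day 1 draw sits under pharmacodynamic sampling.
- Every De Novo subject needs a screening value, because De Novo inclusion criterion 9 requires at least 100 pg/mL.
- The Visit 1 rule in SAP section 6.3 does not argue for Day 1, since NE is taken out of it. The carve-out alone does not prove screening, because the rollover and Day 57 definitions need it too.
- Protocol section 8.1 gives way to the SAP, which does define NE.
- Protocol section 6.4.8 says "NE alone will also be collected at Screening Visit as part of the eligibility criteria evaluations". That states why the sample is drawn and does not bar its use as a baseline.

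**3. What depends on the choice**

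The choice affects the De Novo contribution to the open-label NE summary and to NE subgroup labels. Randomized-withdrawal baseline NE is the Day 57 result either way. SAP section 8.6 applies no multiplicity adjustment outside its testing sequence. Randomization is at Day 113, after both candidate samples.

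**4. How many could change label (illustration on assumed values)**

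- Planned De Novo subjects: 258 - 170 = 88.
- Randomized, assuming the planned 60% applies equally to both groups: 88 × 0.60 = 52.8.
- Assumed NE model: log-normal, median 180 to 500 pg/mL, between-subject CV 60%, within-subject CV 15 to 35%, screening value at least 100 pg/mL. Two draws per subject are compared with 200 pg/mL.

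| Median (pg/mL) | Share changing subgroup, within-subject CV 15% / 25% / 35% |
|---|---|
| 180 | 0.137 / 0.217 / 0.280 |
| 280 | 0.102 / 0.164 / 0.216 |
| 350 | 0.074 / 0.121 / 0.164 |
| 500 | 0.032 / 0.057 / 0.084 |

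Low end: 52.8 × 0.032 = 1.7 subjects, or 1.7/154 = 1.1%. High end: 52.8 × 0.280 = 14.8 subjects, or 14.8/154 = 9.6%. If 20% lacked a Day 1 result, these become 1.7 × 0.8 = 1.4 and 14.8 × 0.8 = 11.8.

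Varying the between-subject CV over 40 to 80% widens the share to 0.013 to 0.333, which is 52.8 × 0.013 = 0.7 to 52.8 × 0.333 = 17.6 subjects. A separate run (median 200 or 300 pg/mL, between-subject log-SD 0.5, within-subject log-SD 0.1 to 0.3) gave 6.6% to 26.3%. Both the NE model and the count of 53 are assumptions. SAP sections 6.4.7 and 8.4.1 also provide for subjects whose participation ended because the sponsor terminated the study, so the actual count may be smaller.

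**The case for a change.** The strongest case for acting is that the samples are not interchangeable and that correcting one sentence costs nothing. Screening values are truncated at 100 pg/mL by eligibility, and Day 1 values are not. Day 1 and Day 57 draws are matched to within an hour by clock time, which the protocol considers important for NE, and no such matching is set for screening. Midodrine and droxidopa need only be off 7 days before Visit 1, so the two draws may be taken under different medication.

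These points are true, but they do not show that Day 1 is the better classifier. The truncation lies well below the 200 pg/mL cut and does not by itself move anyone across it. Time-matching serves the Day 1 to Day 57 pharmacodynamic comparison, which protocol section 8.5.4 sends to a separate report. The documents do not say whether the medication difference changes NE. Nor does consistency with rollover subjects settle it: their bullet has the same form, but which visit supplied the value depends on the Study 0169 schedule, which is not available here.

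What stands is that the wording before the bracket is loose and that the SAP never states that the Day 1 result is set aside.

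**Conclusion.** No change to the plan follows. The bullet combines a loose description with an exact name. The name can be followed, gives one value per De Novo subject, and is probably what was meant. Taking it yields a sound exploratory subgroup analysis. Rewording the bullet to say only screening would tidy the text and change no result. Switching to Day 1 would be a debatable choice with no shown advantage.

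The reach is small: De Novo subjects with both results, the open-label NE summary, and exploratory subgroup labels where the two values fall on opposite sides of 200 pg/mL. Both samples precede randomized treatment, so either choice leaves the comparison within each subgroup unbiased. Rollover subjects, the Day 57 baseline, the primary test, the testing sequence and the sample size are untouched.

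That the two readings differ is certain from the schedule. The number who would change subgroup is not determinable from the documents. The figure of about 2 to 15 of 53 rests wholly on the assumed NE distribution, equal 60% eligibility and complete Day 1 sampling, and its upper end needs a median near the cut.
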